### **6.6 Concomitant Therapy**

Throughout the study, Investigators may prescribe any concomitant medications or treatments deemed necessary to provide adequate supportive care except for those listed in [Section 6.11](#).

Concomitant therapies are to be collected from informed consent through EOS. Therapy name, indication, dose, unit, frequency, route, start date and stop date should be collected.

Acetaminophen (no more than 325 mg per dose and 2 g per day) for analgesia and hormone replacement therapy (eg, estrogen, thyroid hormone) will be allowed. Any herbal medicines, vitamins and supplements consumed by the subject within 30 days prior to receiving the first dose of AMG 986 and continuing use if considered, will be reviewed by the principal investigator and Amgen medical monitor. Written documentation of this review and Amgen acknowledgment are required for subject participation. Details of all concomitant medications will be recorded in the subject's source documents and on the CRF.

Subjects must not consume grapefruit or grapefruit products during the study or within 7 days of study Day 1.

### **6.7 Alcohol and Tobacco Restrictions**

Subjects are not permitted to consume any alcohol while in residence and within 24 hours prior to a study visit (including screening).

During the study, the use of alcohol will be limited to no more than 1 drink per day (1 drink being the equivalent of 12 ounces of regular beer, 5 ounces of wine or 1.5 ounces of 80 proof distilled spirits).

Approved

Subjects are not permitted to use nicotine or tobacco containing products (including but not limited to: snuff, chewing tobacco, cigars, cigarettes, pipes, or nicotine patches) throughout the screening period and for the duration of the study.

There will be no restrictions regarding caffeine intake during the screening period or at any time during the study.

#### **6.8 Other Treatment Procedures**

Not applicable for this study.

#### **6.9 Medical Devices**

Not applicable for this study.

#### **6.10 Product Complaints**

A product complaint is any written, electronic or oral communication that alleges deficiencies related to the identity, quality, durability, reliability, safety, effectiveness, or performance of a drug(s) or device(s) after it is released for distribution to market or clinic by either Amgen or by distributors and partners for whom Amgen manufactures the material. This includes any drug(s), device(s) or combination product (s) provisioned and/or repackaged /modified by Amgen. Drug(s) or device(s) includes investigational product.

Any product complaint(s) associated with an investigational product(s) or non-investigational product(s) or device(s) supplied by Amgen are to be reported according to the instructions provided in the IPIM.

#### **6.11 Excluded Treatments, Medical Device use, and/or Procedures During Study Period**

During the study period, use of strong CYP3A4 inhibitors is not allowed, including (not limited to): macrolide antibiotics (eg, clarithromycin, telithromycin), antifungals (eg, itraconazole, voriconazole), antivirals (eg, ritonavir, saquinavir, indinavir, nelfinavir), nefazodone.

During the study period, ingestion of grapefruit or grapefruit products and other foods that are known to inhibit CYP3A4 is not allowed.

During the study period, use of strong CYP3A4 inducers is not allowed, Including (not limited to): phenytoin, carbamazepine, rifampin, rifabutin, rifapentin, phenobarbital. Subjects should not take St John's Wort.

Approved

During the study period, use of strong P-glycoprotein inhibitors is not allowed, including (not limited to): elacridar and valsopodar.

During the study period, use of PDE5 inhibitors including but not limited to avanafil, sildenafil, tadalafil, vardenafil is not allowed.

During the study period, use of vasodilators that could in the opinion of the investigator potentially lead to a drop in blood pressure in combination with investigational product is not allowed.

## **7. STUDY PROCEDURES**

### **7.1 Schedule of Assessments**

A complete schedule of assessments has been included in [Section 7.1](#).

Refer to the applicable supplemental (eg, laboratory, imaging, ECG) manuals for detailed collection and handling procedures.

Approved

Table 9. Schedule of Assessments for Cohorts 1 & 2 IV Part A

Activity	Screening	Check-in	Treatment Period												
			1												
Study Day	-28 to -2	-1	Pre-dose	0	0.25	0.5	1	1.25	1.5	2	3	4	6	8	12
General & Safety Assessments															
Informed Consent	X														
Residency A		X	X	X	X	X	X	X	X	X	X	X	X	X	X
Medical History	X														
Physical Examination	X	X													
Weight	X	X													
Height	X														
Vital Signs (BP F , HR, RR, TEMP) B	X	X	X		X	X	X	X	X	X	X	X	X	X	X
ECG C	X		X			X	X		X	X		X	X		X
Concomitant Medications	X	X	X	X	X	X	X	X	X	X	X	X	X	X	X
Adverse Events W			X	X	X	X	X	X	X	X	X	X	X	X	X
Serious Adverse Events	X	X	X	X	X	X	X	X	X	X	X	X	X	X	X
Laboratory Assessments															
Chemistry, Hematology, & Urinalysis	X	X													
Troponin I	X		X												
FSH (postmenopausal females only) D	X														
HIV, HepCAb, HBsAg, HBcAb	X														
Drug, Alcohol, & Cotinine Screen	X	X													
Echocardiographic Assessments															
M-mode and 2-D									X				X		
M-mode, 2-D, Flow & Tissue Doppler			X												
Investigational Product Administration															
IP Administration (LD, 1 hr infusion)				X											
Pharmacokinetic Assessments															
AMG 986 Plasma PK Collection			X		X	X	X G	X	X	X	X	X	X	X	X
Cumulative Urine Collection for AMG 986 PK			X H												X I

Approved

Footnotes defined on page 71

**Table 9. Schedule of Assessments for Cohorts 1 & 2 IV Part A**

Activity	Follow Up Period					EOS
	2	3	4	5	14	
Study Day	24	48	72	96		30
Study Time (Hours)						
General & Safety Assessments						
Informed Consent						
Residency A	X	X				
Medical History						
Physical Examination	X	X		X		X
Weight						
Height						
Vital Signs (BP F , HR, RR, TEMP) B	X	X	X	X	X	X
ECG C	X	X				X
Concomitant Medications	X	X	X	X	X	X
Adverse Events W	X	X	X	X	X	X
Serious Adverse Events	X	X	X	X	X	X
Laboratory Assessments						
Chemistry, Hematology, & Urinalysis	X	X		X	X	X
Troponin I	X			X		
FSH (postmenopausal females only) D						
HIV, HepCAb, HBsAg, HBcAb						
Drug, Alcohol, & Cotinine Screen						X
Echocardiographic Assessments						
M-mode and 2-D						
M-mode, 2-D, Flow & Tissue Doppler	X					
Investigational Product Administration						
IP Administration (LD, 1 hr infusion)						
Pharmacokinetic Assessments						
AMG 986 Plasma PK Collection	X	X	X	X		
Cumulative Urine Collection for AMG 986 PK	X J	X K				

Approved

Footnotes defined on page 71

**Table 10. Schedule of Assessments for Cohorts 3 to 5 IV Part A**

Activity	Screening -28 to -2	Check-in -1	Treatment Period									
			Study Day	1								
Study Time (Hours)			Predose	0	0.25	0.5	1	1.25	1.5	2	6	12
General & Safety Assessments												
Informed Consent	X											
Residency A		X	X	X	X	X	X	X	X	X	X	X
Medical History	X											
Physical Examination	X	X										
Weight	X	X										
Height	X											
Vital Signs (BP F , HR, RR, TEMP) B	X	X	X		X	X	X	X	X	X	X	X
ECG C	X		X			X	X		X	X	X	X
Concomitant Medications	X	X	X	X	X	X	X	X	X	X	X	X
Adverse Events W			X	X	X	X	X	X	X	X	X	X
Serious Adverse Events	X	X	X	X	X	X	X	X	X	X	X	X
Laboratory Assessments												
Chemistry, Hematology, & Urinalysis	X	X										
Troponin I	X		X									
FSH (postmenopausal females only) D	X											
HIV, HepCAb, HBsAg, HBcAb	X											
Drug, Alcohol, & Cotinine Screen	X	X										
Echocardiographic Assessments												
M-mode and 2-D									X		X	
M-mode, 2-D, Flow & Tissue Doppler			X									
Investigational Product Administration												
IP Administration (LD, 1 hr infusion)				X								
IP Administration (MD, 23 hr infusion)							X					
Pharmacokinetic Assessments												
AMG 986 Plasma PK Collection			X		X	X	X G	X	X	X	X	X
Cumulative Urine Collection for AMG 986 PK			X H									X I

Approved

Footnotes defined on page 71

**Table 10. Schedule of Assessments for Cohorts 3 to 5 IV Part A**

Activity	Treatment Period									Follow-Up Period					EOS	
	2									3	4	5	6	7		14
Study Day	24	24.25	24.5	25	26	27	29	31	36	48	72	96	120	144		
General & Safety Assessments																
Informed Consent																
Residency A	X	X	X	X	X	X	X	X	X	X						
Medical History																
Physical Examination	X									X		X				X
Weight																
Height																
Vital Signs (BP F , HR, RR, TEMP) B	X	X	X	X	X	X	X	X	X	X	X	X	X	X T	X	X
ECG C	X		X	X	X		X		X	X	X					X
Concomitant Medications	X	X	X	X	X	X	X	X	X	X	X	X	X	X T	X	X
Adverse Events W	X	X	X	X	X	X	X	X	X	X	X	X	X	X T	X	X
Serious Adverse Events	X	X	X	X	X	X	X	X	X	X	X	X	X	X T	X	X
Laboratory Assessments																
Chemistry, Hematology, & Urinalysis	X									X		X			X	X
Troponin I	X											X				
FSH (postmenopausal females only) D																
HIV, HepCAb, HBsAg, HBcAb																
Drug, Alcohol, & Cotinine Screen																X
Echocardiographic Assessments																
M-mode and 2-D							X				X		X U			
M-mode, 2-D, Flow & Tissue Doppler	X									X						
Investigational Product Administration																
IP Administration (LD, 1 hr infusion)																
IP Administration (MD, 23 hr infusion)																
Pharmacokinetic Assessments																
AMG 986 Plasma PK Collection	X G	X	X	X	X	X	X	X	X	X	X	X	X	X T		
Cumulative Urine Collection for AMG 986 PK	X J									X K						

Approved

Footnotes defined on page 71

**Table 11. Schedule of Assessments for Cohorts 1-6 PO Part A**

Activity	Screening -28 to -2	Check-in -1	Treatment Period											Follow Up Period					EOS
			1	2	3	4	5	14	30	2	3	4	5	14	30				
Study Day	-28 to -2	-1	1	2	3	4	5	14	30	2	3	4	5	14	30				
Study Time (Hours)			Pre-dose	0	0.5	1	2	3	4	6	8	12	24	48	72	96			
General & Safety Assessments																			
Informed Consent	X																		
Residency A		X	X	X	X	X	X	X	X	X	X	X	X						
Medical History	X																		
Physical Examination	X	X											X			X	X		
Weight	X	X																	
Height	X																		
Vital Signs (BP F , HR, RR, TEMP) B	X	X	X		X	X	X	X	X	X	X	X	X	X	X	X	X		
ECG C	X		X		X	X	X		X	X		X	X	X			X		
Concomitant Medications	X	X	X	X	X	X	X	X	X	X	X	X	X	X	X	X	X		
Adverse Events W			X	X	X	X	X	X	X	X	X	X	X	X	X	X	X		
Serious Adverse Events	X	X	X	X	X	X	X	X	X	X	X	X	X	X	X	X	X		
Laboratory Assessments																			
Chemistry, Hematology, & Urinalysis	X	X											X			X	X		
Troponin I	X		X										X			X			
FSH (postmenopausal females only) D	X																		
Pregnancy	X	X															X		
HIV, HepCAb, HBsAg, HBcAb	X																		
Drug, Alcohol, & Cotinine Screen	X	X															X		
Echocardiographic Assessments																			
M-mode and 2-D							X			X		X							
M-mode, 2-D, Flow & Tissue Doppler			X										X						
Investigational Product Administration																			
IP Administration				X															
Pharmacokinetic Assessments																			
AMG 986 Plasma PK Collection			X		X	X	X	X	X	X	X	X	X	X	X	X			
Cumulative Urine Collection for AMG 986 PK			X H									X I	X J						

Footnotes defined on page 71

Approved

**Table 12. Schedule of Assessments for IV Cohorts Part B**

Activity	Screening -28 to -2	Check-in -1	Treatment Period												
			1									2	3	4	
Study Day			Pre-dose	0	0.25	0.5	1	1.25	1.5	2	6	12	24	48	72
General & Safety Assessments															
Informed Consent	X														
Residency A		X	X	X	X	X	X	X	X	X	X	X	X	X	X
Medical History	X														
Physical Examination	X	X											X		
Weight	X	X													
Height	X														
Vital Signs (BP F , HR, RR, TEMP) B	X	X	X		X	X	X	X	X	X	X	X	X	X	X
ECG C	X		X			X	X		X	X	X	X	X	X	X
Concomitant Medications	X	X	X	X	X	X	X	X	X	X	X	X	X	X	X
Adverse Events W			X	X	X	X	X	X	X	X	X	X	X	X	X
Serious Adverse Events	X	X	X	X	X	X	X	X	X	X	X	X	X	X	X
Laboratory Assessments															
Chemistry, Hematology, & Urinalysis	X	X													
Troponin I	X		X										X		
Plasma Osmolality			X E										X	X	
Urine Osmolality			X N										X S	X S	
FSH (postmenopausal females only) D	X														
HIV, HepCAb, HBsAg, HBcAb	X														
Drug, Alcohol, & Cotinine Screen	X	X													
Echocardiographic Assessments															
M-mode and 2-D	X										X				X
M-mode, 2-D, Flow & Tissue Doppler			X										X	X	
Investigational Product Administration															
IP Administration (LD, 1 hr infusion)				X											
IP Administration (MD, 23 hr infusion [Day 1])							X								
IP Administration (MD, 24 hr infusion [Days 2-4])													X	X	X
Pharmacokinetic Assessments															
AMG 986 Plasma PK Collection			X		X	X	X G		X	X	X	X	X G	X G	X G
Cumulative Urine Collection for AMG 986 PK			X M												

Approved

Footnotes defined on page 71

**Table 12. Schedule of Assessments for IV Cohorts Part B**

Activity	Follow-Up Period														EOS
	5	5	5	5	5	5	5	5	5	6	7	8	10	14	
Study Day	96	96.25	96.5	97	98	99	101	103	108	120	144	168	216		
Study Time (Hours)	96	96.25	96.5	97	98	99	101	103	108	120	144	168	216		
General & Safety Assessments															
Informed Consent															
Residency A	X	X	X	X	X	X	X	X	X	X					
Medical History															
Physical Examination							X			X				X	X
Weight															
Height															
Vital Signs (BP F , HR, RR, TEMP) B	X	X	X	X	X	X	X	X	X	X	X	X	X	X	X
ECG C	X		X	X	X		X		X	X	X				X
Concomitant Medications	X	X	X	X	X	X	X	X	X	X	X	X	X	X	X
Adverse Events W	X	X	X	X	X	X	X	X	X	X	X	X	X	X	X
Serious Adverse Events	X	X	X	X	X	X	X	X	X	X	X	X	X	X	X
Laboratory Assessments															
Chemistry, Hematology, & Urinalysis	X									X				X	X
Troponin I	X														
Plasma Osmolality	X														
Urine Osmolality	X S														
FSH (postmenopausal females only) D															
HIV, HepCAb, HBsAg, HBcAb															
Drug, Alcohol, & Cotinine Screen															X
Echocardiographic Assessments															
M-mode and 2-D					X			X				X			
M-mode, 2-D, Flow & Tissue Doppler	X									X					X
Investigational Product Administration															
IP Administration (LD, 1 hr infusion)															
IP Administration (MD, 23 hr infusion [Day 1])															
IP Administration (MD, 24 hr infusion [Days 2-4])															
Pharmacokinetic Assessments															
AMG 986 Plasma PK Collection	X G	X	X	X	X	X	X	X	X	X	X	X	X		
Cumulative Urine Collection for AMG 986 PK	X M														

Approved

Footnotes defined on page 71

Table 13. Schedule of Assessments for PO Cohorts Part B

Activity	Screening	Check-in	Treatment Period													
			1										2	3	4	5-6
Study Day	-28 to -2	-1	Pre-dose	0	0.5	1	2	3	4	6	8	12	24 Q	48 Q	72 Q	73-143 Q
General & Safety Assessments																
Informed Consent	X															
Residency A		X	X	X	X	X	X	X	X	X	X	X	X	X	X	X
Medical History	X															
Physical Examination	X	X											X			
Weight	X	X														
Height	X															
Vital Signs (BP F , HR, RR, TEMP) B	X	X	X		X	X	X	X	X	X	X	X	X	X	X	X
ECG C	X		X		X	X	X		X	X		X	X			
Concomitant Medications	X	X	X	X	X	X	X	X	X	X	X	X	X	X	X	X
Adverse Events W			X	X	X	X	X	X	X	X	X	X	X	X	X	X
Serious Adverse Events	X	X	X	X	X	X	X	X	X	X	X	X	X	X	X	X
Laboratory Assessments																
Chemistry, Hematology, & Urinalysis	X	X											X			X P
Troponin I	X		X										X			X R
Plasma Osmolality			X E										X			
Urine Osmolality			X N										X S			
FSH (postmenopausal females only) D	X															
Pregnancy	X	X														
HIV, HepCAb, HBsAg, HBcAb	X															
Drug, Alcohol, & Cotinine Screen	X	X														
Echocardiographic Assessments																
M-mode and 2-D	X						X			X						
M-mode, 2-D, Flow & Tissue Doppler			X										X			
Investigational Product Administration																
IP Administration L				X									X	X	X	X
Pharmacokinetic Assessments																
AMG 986 Plasma PK Collection			X		X	X	X	X	X	X	X	X	X	X	X	
Cumulative Urine Collection for AMG 986 PK			X M													

Approved

Footnotes defined on page 71

Table 13. Schedule of Assessments for PO Cohorts Part B

Activity	Treatment Period										Follow-Up Period						EOS
	7										8	9	10	11	14	21	
Study Day	144 Q	144.5	145	146	147	148	150	152	156	168	192	216	240				
General & Safety Assessments																	
Informed Consent																	
Residency A	X	X	X	X	X	X	X	X	X	X							
Medical History																	
Physical Examination	X									X				X	X	X	
Weight																	
Height																	
Vital Signs (BP F , HR, RR, TEMP) B	X	X	X	X	X	X	X	X	X	X	X	X	X	X	X	X	X
ECG C	X	X	X	X		X	X		X	X	X			X	X	X	X
Concomitant Medications	X	X	X	X	X	X	X	X	X	X	X	X	X	X	X	X	X
Adverse Events W	X	X	X	X	X	X	X	X	X	X	X	X	X	X	X	X	X
Serious Adverse Events	X	X	X	X	X	X	X	X	X	X	X	X	X	X	X	X	X
Laboratory Assessments																	
Chemistry, Hematology, & Urinalysis	X									X				X	X	X	
Troponin I										X		X					
Plasma Osmolality	X																
Urine Osmolality	X S																
Pregnancy D																	X
FSH (postmenopausal females only) D																	
HIV, HepCAb, HBsAg, HBcAb																	
Drug, Alcohol, & Cotinine Screen														X	X	X	
Echocardiographic Assessments																	
M-mode and 2-D				X								X		X	X		
M-mode, 2-D, Flow & Tissue Doppler	X									X							X O
Investigational Product Administration																	
IP Administration L	X																
Pharmacokinetic Assessments																	
AMG 986 Plasma PK Collection	X	X	X	X	X	X	X	X	X	X	X	X	X				
Cumulative Urine Collection for AMG 986 PK										X K							

Approved

Footnotes defined on page 71

- A Subjects in study Parts A and B will remain in-house from Day -1 through the completion of all assessments designated in the SOA.
- B Vital signs will be performed pre-dose for each day in residency and at time points in the SOA.
- C ECGs will be performed on Day 1 pre-dose. Study eligibility QTc must be < 450 msec as mentioned in [section 122](#). Consultation with the medical monitor is required prior to dosing if QTc > 450 msec on Day 1 pre-dose. At screening a single ECG will be performed. At baseline, ECGs will be performed on 3 occasions separated by at least 30 minutes all in triplicate for a total of 9 ECGs. At all other time points ECGs will be performed in a standardized method, in triplicate and approximately 30 seconds apart, prior to blood draws or other invasive procedures.
- D Female subjects only.
- E Should be collected for subjects who qualify for enrollment.
- F BP measurements will be obtained in triplicate approximately 2 minutes apart in a semi-Fowler position at pre-dose and at time points corresponding to ECG monitoring.
- G PK sample collection to occur just prior to the end of infusion.
- H Urine sample obtained at pre-dose void collection (5mL to 10mL aliquot).
- I Aliquot (5mL to 10mL) of cumulative urine collection (0h to 12h) taken for PK sample.
- J Aliquot (5mL to 10mL) of cumulative urine collection (12h to 24h) taken for PK sample.
- K Aliquot (5mL to 10mL) of cumulative urine collected over past 24h taken for PK.
- L Once daily PO AMG 986/placebo administration for 7 consecutive days.
- M Aliquot (5mL to 10mL) of 24h urine collection taken for PK sample.
- N Cumulative collection of urine over past 24 h required for baseline assessment. Required for subjects who meet eligibility requirements for enrollment. Not a requirement to assess eligibility for enrollment.
- O This assessment will be performed only if deemed necessary by the investigator upon review of the prior assessment.
- P Chemistry, Hematology, & Urinalysis to be collected on Day 5.
- Q Procedures to be completed prior to dosing: physical examination, vital signs, ECGs, laboratory assessments, echocardiographic assessments, pharmacokinetic assessments.
- R Troponin I to be collected on Day 5.
- S Cumulative collection of urine over past 24 h required for osmolality assessment
- T To be collected for only Cohort 5 IV Part A
- U To be collected for only Cohorts 4 and 5 IV Part A
- V If dose is reduced, patients will be observed for at least 6 hours after the first administration of a new dose
- W Adverse events possibly related to any study procedures/study activity are reported from signing of the ICF.

Approved

**Table 14. Schedule of Assessments for Patient Cohort Part C**

Activity Study Day	10 mg PO Treatment													
	-28 to -2 k	-1	1					2	3	4	5	6	7	
Study Time (Hours)			Pre-dose	0	1	2	4	6	24 G	48 G	72 G	96 G	120 G	144 G
General & Safety Assessments														
Informed Consent J	X													
Medical History	X													
Physical Examination	X	X							X					
Weight	X	X												
Height	X													
Vital Signs (BP E , HR, RR, TEMP) A	X	X	X		X	X		X	X	X	X	X	X	X
ECG B	X		X		X	X	X	X						
Concomitant Medications														
Adverse Events I														
Serious Adverse Events														
Laboratory Assessments														
Chemistry, Hematology, & Urinalysis	X	X							X					
Troponin I	X		X						X		X			
NT-proBNP	X													
FSH (postmenopausal females only) C	X													
Pregnancy C	X	X												
HIV, HepCAb, HBsAg, HBcAb	X													
Drug, Alcohol, & Cotinine Screen	X	X												
Echocardiographic Assessments														
M-mode, 2-D, Flow & Tissue Doppler	X		X					X			X			
Investigational Product AdministrationE														
IP Administration PO (10 mg, Days 1-7)				X					X	X	X	X	X	X
Pharmacokinetic/Biomarker Assessments														
AMG 986 Plasma PK Collection			X		X	X	X	X	X					
Plasma and Serum Biomarker Collection			X											
Cell Pellet Collection			X											

Approved

Footnotes defined on page 75

**Table 14. Schedule of Assessments for Patient Cohort Part C**

Activity Study Day	30 mg PO									
	8				9	10	11	12	13	14
Study Time (Hours)	168 G (Predose)	170	172	174	192 G	216 G	240 G	264 G	288 G	312 G
General & Safety Assessments										
Informed Consent										
Medical History										
Physical Examination										
Weight										
Height										
Vital Signs (BP E , HR, RR, TEMP) A	X		X		X	X	X	X	X	X
ECG B		X		X						
Concomitant Medications										
Adverse Events I										
Serious Adverse Events										
Laboratory Assessments										
Chemistry, Hematology, & Urinalysis	X				X					
Troponin I	X									X
NT-proBNP										
FSH (postmenopausal females only) C										
Pregnancy C										
HIV, HepCAb, HBsAg, HBcAb										
Drug, Alcohol, & Cotinine Screen										
Echocardiographic Assessments										
M-mode, 2-D, Flow & Tissue Doppler	X			X			X			
Investigational Product Administration										
IP Administration PO (30 mg, Days 8-14) E	X				X	X	X	X	X	X
Pharmacokinetic/Biomarker Assessments										
AMG 986 Plasma PK Collection	X	X	X	X	X					
Plasma and Serum Biomarker Collection	X									
Cell Pellet Collection										

Approved

Footnotes defined on page 75

**Table 14. Schedule of Assessments for Patient Cohort Part C**

Activity Study Day	100 mg											EOS 30
	15 Predose					16	17	18	19	20	21	
Study Time (Hours)	336 G	337	338	340	342	360 G	384 G	408 G	432 G	456 G	480 G	
General & Safety Assessments												
Informed Consent												
Medical History												
Physical Examination	X										X	X
Weight												
Height												
Vital Signs (BP E HR, RR, TEMP) A	X	X		X		X	X	X	X	X	X	X
ECG B	X	X	X		X							X
Concomitant Medications												
Adverse Events I												
Serious Adverse Events												
Laboratory Assessments												
Chemistry, Hematology, & Urinalysis	X					X					X	X
Troponin I												X
NT-proBNP												
FSH (postmenopausal females only) C												
Pregnancy C												X
HIV, HepCAb, HBsAg, HBcAb												
Drug, Alcohol, & Cotinine Screen												
Echocardiographic Assessments												
M-mode, 2-D, Flow & Tissue Doppler	X				X			X			X	X
Investigational Product Administration												
IP Administration PO (100 mg, Days 15-21) E	X					X	X	X	X	X	X	
Pharmacokinetic/Biomarker Assessments												
AMG 986 Plasma PK Collection	X	X	X	X	X	X					X	
Plasma and Serum Biomarker Collection	X										X	
Cell Pellet Collection												

Approved

Footnotes defined on page 75

- 
- A Vital signs will be performed pre-dose for each day and at time points in the SOA.
  - B ECGs will be performed on Day 1 pre-dose and may be repeated. . At screening a single ECG will be performed. At baseline, a single ECG will be performed. . At all other time points single ECGs will be performed in a standardized method, and prior to blood draws or other invasive procedures.
  - C Female subjects only.
  - D BP measurements will be obtained in a semi-Fowler position at pre-dose and at time points listed in the SOA.
  - E Once daily PO AMG 986/placebo administration for 7 consecutive days.
  - F This assessment will be performed only if deemed necessary by the investigator upon review of the prior assessment.
  - G Procedures to be completed prior to dosing: physical examination, vital signs, ECGs, laboratory assessments, echocardiographic assessments, pharmacokinetic assessments.
  - H If dose is reduced, patients will be observed for at least 6 hours after the first administration of a new dose
  - I Adverse events possibly related to any study procedures/study activity are reported from signing of the ICF.
  - J At the discretion of the PI and with safety considerations paramount, subjects may undergo study procedures on an inpatient basis.
  - K Screening and Day -1 activities may be performed on the same day.

Approved

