#### **7.2.15 Clinical Chemistry**

Blood samples for clinical chemistry will be collected at the time points specified in the Schedule of Assessments ([Section 7.1](#)). Baseline assessments will be taken on Day-1.

All laboratory tests must be reviewed and signed by the principal investigator or qualified designee. Additional safety laboratory assessments may be performed for subject safety.

The tests listed in

[Table 16](#) will be conducted and analyzed by standard laboratory procedures.

Approved

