#### **10.5.4.5 AMG 986 Impact on Heart Failure Prognostics**

If data allow, heart failure prognostic markers, eg, NT-pro-BNP, Troponin, Galectin-3, soluble ST2 and GDF-15 will be measured in patients in Part C after dosing with AMG 986 and summarized as changes from baseline over time.

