### Rationale:

The primary objective of this protocol amendment is to enhance safety assessments of subjects during the study:

1. Include an unblinded medical monitor to review adverse events in real-time
2. Add the collection of laboratory assessments at 24 hours and discharge
3. Add the assessment of troponin levels at baseline prior to dosing, Days 2 and 5
4. Add the requirement to evaluate AMG 986 exposure and dose predictions using available human PK data and include in the review of dose cohorts by DLRM members.
5. Add a physical exam at 24 hours

Minor administrative, typographical, and grammatical changes were made.

Approved

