##### 10.5.2 Laboratory Test Results

Laboratory analytes are provided in the protocol Table 13. Summary tables of **selected** chemistry and hematology data and changes from baseline over time will be provided for each protocol scheduled visit by **pooled AMG 986 and pooled placebo treatment groups for part A and part B of the study and by each treatment group for each cohort HFrEF and HFpEF for part C of the study.**

Number and percentage of subjects of each troponin status “undetected”, “detected” and “elevated” at each scheduled assessment may be summarized **in a similar way as laboratory summaries.** Summaries will also be presented treating troponin as a

continuous variable **in a similar way as laboratory summaries**. Troponin values below or above quantifiable limits will be treated as equal to the limits.

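### Part C has no dedicated Troponin I time point during the 100 mg week, and Tables 14 and 16 conflict on whether the chemistry draws cover it

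*Protocol*

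**What the plan says.** - **Dosing.** Protocol Table 14 gives 10 mg on Days 1-7, then "IP Administration PO (30 mg, Days 8-14", then "IP Administration PO (100 mg, Days 15-21".
- **Troponin I row, Table 14.** It is marked at screening, Day 1 pre-dose, 24 h and 72 h on the 10 mg page, and at 168 h (Day 8 pre-dose) and 312 h (Day 14) on the 30 mg page. On the 100 mg page the only mark is at the end-of-study visit, Day 30.
- **Timing.** Footnote G places laboratory samples on the flagged days before that day's dose.
- **Chemistry.** The row "Chemistry, Hematology, & Urinalysis" on the 100 mg page is marked at 336, 360 and 480 h (Days 15, 16 and 21) and at end of study. Protocol 7.2.15 says "Blood samples for clinical chemistry will be collected at the time points specified in the Schedule of Assessments" and refers to Table 16 for the tests. Table 16 puts Troponin I in its Chemistry column.
- **Biomarkers.** The row "Plasma and Serum Biomarker Collection" is marked on Day 15 pre-dose and Day 21. Protocol 10.5.4.5 says that "heart failure prognostic markers, eg, NT-pro-BNP, Troponin, Galectin-3, soluble ST2 and GDF-15 will be measured in patients in Part C after dosing", subject to the data allowing it.
- **Analysis.** SAP 10.5.2 has "Number and percentage of subjects of each troponin status" as a possible summary at each scheduled assessment, and adds a continuous summary. Both sit under the safety analyses. SAP 10.7 drops the exploratory endpoints and keeps only NT-proBNP plots and a listing for the HFrEF cohort.

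**The concern.** The primary objective includes the safety of ascending doses in heart failure patients, and clinically significant laboratory changes are part of a primary endpoint. Troponin I is the one laboratory marker with its own repeated post-dose row in Part C, and that row stops before the top dose starts. If sites follow it, a transient rise during the third week goes unrecorded. The dose level review at the end of the 21 days would then have nothing later than Day 14, and the by-visit troponin summary would have no on-treatment value at 100 mg in either cohort. If some sites instead run Troponin I with every chemistry draw, the 100 mg values would exist for some patients and not others, for reasons unrelated to the patient.

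**Working it through.** No power or error-rate figure is involved. The check is a count of marks, assigned to the dose on board using footnote G.

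**Step 1: column check.** The 100 mg page has 12 time columns. The single Troponin I mark is in the twelfth (Day 30). The Pregnancy row has its only mark in the same column, and the Chemistry row fills 336, 360 and 480 h and Day 30. A shifted row is therefore unlikely.

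**Step 2: post-dose marks by dose on board.** A pre-dose sample on Day 8 reflects 10 mg, and one on Day 15 reflects 30 mg.

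| Dose on board | Troponin I row | Chemistry row |
|---|---|---|
| 10 mg | 24, 72, 168 h = 3 | 24, 168 h = 2 |
| 30 mg | 312 h = 1 | 192, 336 h = 2 |
| 100 mg | none = 0 | 360, 480 h = 2 |

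The Day 16 sample follows one 100 mg dose and the Day 21 sample follows six.

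**Step 3: gaps.** Last dose to next mark: 30 − 21 = 9 days. Between consecutive marks: 30 − 14 = 16 days, which spans the whole 100 mg week.

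**Step 4: the same count if Table 16 is read as a panel run at every chemistry draw.** Taking the union of the two columns above:
- 10 mg: 24, 72, 168 h = 3
- 30 mg: 192, 312, 336 h = 3
- 100 mg: 360, 480 h = 2

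So the number of Troponin I results on 100 mg is 0 or 2 per patient, depending on which table the site follows.

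**Step 5: which reading fits the protocol better.** Table 14 marks Chemistry and Troponin I separately at four shared times (screening, 24 h, 168 h, Day 30). Those Troponin I marks would be redundant if chemistry always included it. NT-proBNP is also in the Chemistry column of Table 16, yet has its own Part C row marked only at screening. Plasma osmolality is in that column too, with its own rows in Part B and none in Part C. Table 16 therefore looks like a list of all analytes, not a per-visit panel. This is an inference; no sentence in the protocol says so.

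**Step 6: do other assessments thin?** Marks with 30 mg on board (170 to 336 h) against 100 mg on board (337 to 480 h):

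| Assessment | 30 mg | 100 mg |
|---|---|---|
| ECG | 170, 174, 336 h = 3 | 337, 338, 342 h = 3 |
| Echocardiography | 174, 240, 336 h = 3 | 342, 408, 480 h = 3 |
| Chemistry | 2 | 2 |
| Physical examination | 336 h = 1 | 480 h = 1 |
| PK | 170, 172, 174, 192, 336 h = 5 | 337, 338, 340, 342, 360, 480 h = 6 |

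Counted by table page, excluding Day 30, the 100 mg page is denser: ECG 2 against 4, chemistry 2 against 3, echocardiography 3 against 4, PK 5 against 7, physical examination 0 against 2. On either count, of these rows only troponin falls.

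**Step 7: exposure.** Table 3 single oral doses in healthy subjects, 100 mg over 30 mg: Cmax 5760 / 1850 = 3.1; AUC 34100 / 12600 = 2.7.

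**The case against.** The strongest reply is that a blank row in Table 14 does not prove that nothing is measured. The NT-proBNP row is blank after screening, yet the protocol plans change from baseline in NT-proBNP and SAP 10.7 plots it. Those later values must come from the biomarker or chemistry draws, and troponin could come the same way. Read literally, 7.2.15 with Table 16 puts Troponin I in the Day 16 and Day 21 chemistry. Protocol 7.7 also lets any collected sample be used for protocol tests. In addition, the Adverse Events and Concomitant Medications rows of Table 14 show no marks although other sections require collection, so a missing mark deserves caution. Part B oral cohorts had Troponin I at 24 h, Day 5 and 168 h (24 h after the last dose) up to 650 mg daily, and the accumulated clinical data were reviewed without an identified safety concern.

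Much of this stands. A reader might infer that troponin is never read at 100 mg. The documents support only that no dedicated time point is scheduled. A reader might also infer that safety sampling in general is thinnest at the highest exposure; step 6 shows that it is not.

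The reply does not remove the conflict between the two tables. The biomarker route gives one sample on 100 mg (Day 21), is conditional and exploratory, and has no troponin analysis under SAP 10.7. The Part B data come from healthy subjects. The Amendment 1 entry "Add the assessment of troponin levels at baseline prior to dosing, Days 2 and 5" lists troponin apart from other laboratory assessments, but it predates Part C and settles nothing about Table 14.

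**Conclusion.** The point holds as a scheduling gap combined with an internal conflict, and it is worth correcting because correction is cheap. Table 14 has 0 Troponin I marks on the seven days of 100 mg, against three on-dose marks at 10 mg and one at 30 mg, with the next mark 9 days after the last dose. Table 16 can be read to supply two. The protocol's structure favours the first reading without settling it.

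The conclusion rests on the table as extracted (supported by the Pregnancy and Chemistry rows) and on footnote G applying to all flagged days. At full enrolment it would touch 2 × 15 = 30 patients on AMG 986 and 2 × 5 = 10 on placebo. The study was discontinued early, so the actual number may be smaller. The documents do not show that any rise was missed. A Day 21 result would inform the end-of-dosing review and the report, but not escalation in that patient.

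**What to change.** 1. **Protocol.** Reconcile Table 14 with Table 16 by marking Troponin I at Day 16 (360 h) and Day 21 (480 h), where chemistry is already drawn. State in 7.2.15 whether Table 16 is a list of analytes or a panel run at every chemistry visit.
2. **SAP 10.5.2.** Include both time points in the Part C troponin summaries, for each treatment group within the HFrEF and HFpEF cohorts.
3. **Patients already treated.** State in the SAP and the report whether any troponin result on 100 mg exists, from which draw (chemistry or biomarker), and for how many patients. Given the early stop, this may be the only part that can still take effect.

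**Cost.** Two extra assays per patient, at most 2 × 40 = 80 at full enrolment, a table edit, and some incidental elevations to follow up in a heart failure population. That no extra blood draw is needed assumes the chemistry tube suits the troponin assay; the laboratory manual is not among the documents.
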